 PROTOCOL 405-201-00013

17 OF 48

STAT-6.1.2
 Residual by Week from Proc Mixed for Change from Baseline in AISRS Total Score, Primary Efficacy Analysis Model
 (Efficacy Sample)

 ----- Analysis Visit (N)=21 -----

The UNIVARIATE Procedure
 Variable: RESID (Residual)

Moments

N	391	Sum Weights	391
Mean	-0.1603789	Sum Observations	-62.708169
Std Deviation	8.75757561	Variance	76.6951306
Skewness	-0.7967468	Kurtosis	0.37509191
Uncorrected SS	29921.158	Corrected SS	29911.101
Coeff Variation	-5460.5518	Std Error Mean	0.44288964

Basic Statistical Measures

Location		Variability	
Mean	-0.16038	Std Deviation	8.75758
Median	1.40218	Variance	76.69513
Mode	-4.23564	Range	49.66442
		Interquartile Range	11.21801

Note: The mode displayed is the smallest of 3 modes with a count of 2.

FILE: normalitybc.lis, RUN: 18JUN2020 10:00
 PROGRAM: /opt/sas/Data/DAP/EB1020/P40520100013/STAT/Program.dev/DOC_STAT/normality.sas
 OPDC, NEW DRUG APPLICATION, IND # 119,361 CENTANAFADINE STAT-6.1.2 FINAL

CENTANAFADINE
 PROTOCOL 405-201-00013

18 OF 48

STAT-6.1.2
 Residual by Week from Proc Mixed for Change from Baseline in AISRS Total Score, Primary Efficacy Analysis Model
 (Efficacy Sample)

 ----- Analysis Visit (N)=21 -----

The UNIVARIATE Procedure
 Variable: RESID (Residual)

Tests for Location: Mu0=0

Test	-Statistic-	-----p Value-----	
Student's t	t -0.36212	Pr > t	0.7175
Sign	M 24.5	Pr >= M	0.0151
Signed Rank	S 2593	Pr >= S	0.2467

Tests for Normality

Test	--Statistic---	-----p Value-----	
Shapiro-Wilk	W 0.95566	Pr < W	<0.0001
Kolmogorov-Smirnov	D 0.082594	Pr > D	<0.0100
Cramer-von Mises	W-Sq 0.827025	Pr > W-Sq	<0.0050
Anderson-Darling	A-Sq 5.002996	Pr > A-Sq	<0.0050

FILE: normalitybc.lis, RUN: 18JUN2020 10:00
 PROGRAM: /opt/sas/Data/DAP/EB1020/P40520100013/STAT/Program.dev/DOC_STAT/normality.sas
 OPDC, NEW DRUG APPLICATION, IND # 119,361 CENTANAFADINE STAT-6.1.2 FINAL

CENTANAFADINE
PROTOCOL 405-201-00013

19 OF 48

STAT-6.1.2
Residual by Week from Proc Mixed for Change from Baseline in AISRS Total Score, Primary Efficacy Analysis Model
(Efficacy Sample)

----- Analysis Visit (N)=21 -----

The UNIVARIATE Procedure
Variable: RESID (Residual)

Quantiles (Definition 5)

Level	Quantile
100% Max	17.73069
99%	14.32811
95%	11.25169
90%	9.52209
75% Q3	6.20743
50% Median	1.40218
25% Q1	-5.01058
10%	-12.76245
5%	-17.32377
1%	-23.46337
0% Min	-31.93373

FILE: normalitybc.lis, RUN: 18JUN2020 10:00
PROGRAM: /opt/sas/Data/DAP/EB1020/P40520100013/STAT/Program.dev/DOC_STAT/normality.sas
OPDC, NEW DRUG APPLICATION, IND # 119,361 CENTANAFADINE STAT-6.1.2 FINAL

CENTANAFADINE
PROTOCOL 405-201-00013

20 OF 48

STAT-6.1.2
Residual by Week from Proc Mixed for Change from Baseline in AISRS Total Score, Primary Efficacy Analysis Model
(Efficacy Sample)

----- Analysis Visit (N)=21 -----

The UNIVARIATE Procedure
Variable: RESID (Residual)

Extreme Observations

-----Lowest-----			-----Highest-----		
Value	USUBJID	Obs	Value	USUBJID	Obs
-31.9337	40520100013	988	14.1209	40520100013	1020
-30.9690	40520100013	1101	14.3281	40520100013	1146
-24.7107	40520100013	1129	14.3988	40520100013	1192
-23.4634	40520100013	865	15.9977	40520100013	958
-22.6585	40520100013	952	17.7307	40520100013	955

FILE: normalitybc.lis, RUN: 18JUN2020 10:00
PROGRAM: /opt/sas/Data/DAP/EB1020/P40520100013/STAT/Program.dev/DOC_STAT/normality.sas
OPDC, NEW DRUG APPLICATION, IND # 119,361 CENTANAFADINE STAT-6.1.2 FINAL

CENTANAFADINE
 PROTOCOL 405-201-00013

21 OF 48

STAT-6.1.2
 Residual by Week from Proc Mixed for Change from Baseline in AISRS Total Score, Primary Efficacy Analysis Model
 (Efficacy Sample)

 ----- Analysis Visit (N)=21 -----

The UNIVARIATE Procedure
 Variable: STUDENTRESID (Studentized Residual)

Moments

N	391	Sum Weights	391
Mean	-0.0173302	Sum Observations	-6.7761143
Std Deviation	1.0026023	Variance	1.00521137
Skewness	-0.7767798	Kurtosis	0.33565986
Uncorrected SS	392.149864	Corrected SS	392.032433
Coeff Variation	-5785.2846	Std Error Mean	0.05070378

Basic Statistical Measures

Location		Variability	
Mean	-0.01733	Std Deviation	1.00260
Median	0.15766	Variance	1.00521
Mode	-0.47523	Range	5.64738
		Interquartile Range	1.29404

Note: The mode displayed is the smallest of 3 modes with a count of 2.

FILE: normalitybc.lis, RUN: 18JUN2020 10:00
 PROGRAM: /opt/sas/Data/DAP/EB1020/P40520100013/STAT/Program.dev/DOC_STAT/normality.sas
 OPDC, NEW DRUG APPLICATION, IND # 119,361 CENTANAFADINE STAT-6.1.2 FINAL

CENTANAFADINE
 PROTOCOL 405-201-00013

22 OF 48

STAT-6.1.2
 Residual by Week from Proc Mixed for Change from Baseline in AISRS Total Score, Primary Efficacy Analysis Model
 (Efficacy Sample)

 ----- Analysis Visit (N)=21 -----

The UNIVARIATE Procedure
 Variable: STUDENTRESID (Studentized Residual)

Tests for Location: Mu0=0

Test	-Statistic-	-----p Value-----
Student's t	t -0.34179	Pr > t 0.7327
Sign	M 24.5	Pr >= M 0.0151
Signed Rank	S 2567	Pr >= S 0.2515

Tests for Normality

Test	--Statistic---	-----p Value-----
Shapiro-Wilk	W 0.957454	Pr < W <0.0001
Kolmogorov-Smirnov	D 0.082316	Pr > D <0.0100
Cramer-von Mises	W-Sq 0.809936	Pr > W-Sq <0.0050
Anderson-Darling	A-Sq 4.874627	Pr > A-Sq <0.0050

FILE: normalitybc.lis, RUN: 18JUN2020 10:00
 PROGRAM: /opt/sas/Data/DAP/EB1020/P40520100013/STAT/Program.dev/DOC_STAT/normality.sas
 OPDC, NEW DRUG APPLICATION, IND # 119,361 CENTANAFADINE STAT-6.1.2 FINAL

CENTANAFADINE
PROTOCOL 405-201-00013

23 OF 48

STAT-6.1.2
Residual by Week from Proc Mixed for Change from Baseline in AISRS Total Score, Primary Efficacy Analysis Model
(Efficacy Sample)

----- Analysis Visit (N)=21 -----

The UNIVARIATE Procedure
Variable: STUDENTRESID (Studentized Residual)

Quantiles (Definition 5)

Level	Quantile
100% Max	2.056753
99%	1.617161
95%	1.320311
90%	1.079049
75% Q3	0.709824
50% Median	0.157662
25% Q1	-0.584218
10%	-1.446331
5%	-2.015562
1%	-2.649605
0% Min	-3.590625

FILE: normalitybc.lis, RUN: 18JUN2020 10:00
PROGRAM: /opt/sas/Data/DAP/EB1020/P40520100013/STAT/Program.dev/DOC_STAT/normality.sas
OPDC, NEW DRUG APPLICATION, IND # 119,361 CENTANAFADINE STAT-6.1.2 FINAL

CENTANAFADINE
 PROTOCOL 405-201-00013

24 OF 48

STAT-6.1.2
 Residual by Week from Proc Mixed for Change from Baseline in AISRS Total Score, Primary Efficacy Analysis Model
 (Efficacy Sample)

 ----- Analysis Visit (N)=21 -----

The UNIVARIATE Procedure
 Variable: STUDENTRESID (Studentized Residual)

Extreme Observations

-----Lowest-----			-----Highest-----		
Value	USUBJID	Obs	Value	USUBJID	Obs
-3.59062	40520100013-	988	1.61159	40520100013-	1146
-3.51155	40520100013-	1101	1.61716	40520100013-	1020
-2.83912	40520100013-	1129	1.63078	40520100013-	1192
-2.64961	40520100013-	865	1.99613	40520100013-	958
-2.63088	40520100013-	952	2.05675	40520100013-	955

 FILE: normalitybc.lis, RUN: 18JUN2020 10:00
 PROGRAM: /opt/sas/Data/DAP/EB1020/P40520100013/STAT/Program.dev/DOC_STAT/normality.sas
 OPDC, NEW DRUG APPLICATION, IND # 119,361 CENTANAFADINE STAT-6.1.2 FINAL

CENTANAFADINE
 PROTOCOL 405-201-00013

25 OF 48

STAT-6.1.2
 Residual by Week from Proc Mixed for Change from Baseline in AISRS Total Score, Primary Efficacy Analysis Model
 (Efficacy Sample)

 ----- Analysis Visit (N)=28 -----

The UNIVARIATE Procedure
 Variable: RESID (Residual)

Moments

N	370	Sum Weights	370
Mean	-0.4073769	Sum Observations	-150.72947
Std Deviation	10.1669831	Variance	103.367545
Skewness	-0.7010249	Kurtosis	0.12558616
Uncorrected SS	38204.0278	Corrected SS	38142.6241
Coeff Variation	-2495.7189	Std Error Mean	0.52855628

Basic Statistical Measures

Location		Variability	
Mean	-0.40738	Std Deviation	10.16698
Median	1.71750	Variance	103.36754
Mode	7.54797	Range	54.45127
		Interquartile Range	14.48720

Note: The mode displayed is the smallest of 2 modes with a count of 2.

FILE: normalitybc.lis, RUN: 18JUN2020 10:00
 PROGRAM: /opt/sas/Data/DAP/EB1020/P40520100013/STAT/Program.dev/DOC_STAT/normality.sas
 OPDC, NEW DRUG APPLICATION, IND # 119,361 CENTANAFADINE STAT-6.1.2 FINAL

CENTANAFADINE
 PROTOCOL 405-201-00013

26 OF 48

STAT-6.1.2
 Residual by Week from Proc Mixed for Change from Baseline in AISRS Total Score, Primary Efficacy Analysis Model
 (Efficacy Sample)

 ----- Analysis Visit (N)=28 -----

The UNIVARIATE Procedure
 Variable: RESID (Residual)

Tests for Location: Mu0=0

Test	-Statistic-	-----p Value-----	
Student's t	t -0.77074	Pr > t	0.4414
Sign	M 25	Pr >= M	0.0108
Signed Rank	S 1007.5	Pr >= S	0.6252

Tests for Normality

Test	--Statistic---	-----p Value-----	
Shapiro-Wilk	W 0.959992	Pr < W	<0.0001
Kolmogorov-Smirnov	D 0.090634	Pr > D	<0.0100
Cramer-von Mises	W-Sq 0.856785	Pr > W-Sq	<0.0050
Anderson-Darling	A-Sq 4.871079	Pr > A-Sq	<0.0050

FILE: normalitybc.lis, RUN: 18JUN2020 10:00
 PROGRAM: /opt/sas/Data/DAP/EB1020/P40520100013/STAT/Program.dev/DOC_STAT/normality.sas
 OPDC, NEW DRUG APPLICATION, IND # 119,361 CENTANAFADINE STAT-6.1.2 FINAL

CENTANAFADINE
PROTOCOL 405-201-00013

27 OF 48

STAT-6.1.2
Residual by Week from Proc Mixed for Change from Baseline in AISRS Total Score, Primary Efficacy Analysis Model
(Efficacy Sample)

----- Analysis Visit (N)=28 -----

The UNIVARIATE Procedure
Variable: RESID (Residual)

Quantiles (Definition 5)

Level	Quantile
100% Max	20.54164
99%	18.23384
95%	12.28388
90%	10.47477
75% Q3	7.54797
50% Median	1.71750
25% Q1	-6.93923
10%	-14.81352
5%	-20.55486
1%	-29.58661
0% Min	-33.90962

FILE: normalitybc.lis, RUN: 18JUN2020 10:00
PROGRAM: /opt/sas/Data/DAP/EB1020/P40520100013/STAT/Program.dev/DOC_STAT/normality.sas
OPDC, NEW DRUG APPLICATION, IND # 119,361 CENTANAFADINE STAT-6.1.2 FINAL

CENTANAFADINE
 PROTOCOL 405-201-00013

28 OF 48

STAT-6.1.2
 Residual by Week from Proc Mixed for Change from Baseline in AISRS Total Score, Primary Efficacy Analysis Model
 (Efficacy Sample)

 ----- Analysis Visit (N)=28 -----

The UNIVARIATE Procedure
 Variable: RESID (Residual)

Extreme Observations

-----Lowest-----			-----Highest-----		
Value	USUBJID	Obs	Value	USUBJID	Obs
-33.9096	40520100013-	1498	18.2304	40520100013-	1344
-31.7656	40520100013-	1517	18.2338	40520100013-	1519
-31.3573	40520100013-	1478	19.0985	40520100013-	1518
-29.5866	40520100013-	1372	20.0136	40520100013-	1589
-28.0541	40520100013-	1504	20.5416	40520100013-	1341

 FILE: normalitybc.lis, RUN: 18JUN2020 10:00
 PROGRAM: /opt/sas/Data/DAP/EB1020/P40520100013/STAT/Program.dev/DOC_STAT/normality.sas
 OPDC, NEW DRUG APPLICATION, IND # 119,361 CENTANAFADINE STAT-6.1.2 FINAL

CENTANAFADINE
 PROTOCOL 405-201-00013

29 OF 48

STAT-6.1.2
 Residual by Week from Proc Mixed for Change from Baseline in AISRS Total Score, Primary Efficacy Analysis Model
 (Efficacy Sample)

 ----- Analysis Visit (N)=28 -----

The UNIVARIATE Procedure
 Variable: STUDENTRESID (Studentized Residual)

Moments

N	370	Sum Weights	370
Mean	-0.040986	Sum Observations	-15.164837
Std Deviation	1.01442638	Variance	1.02906089
Skewness	-0.6955724	Kurtosis	0.11422617
Uncorrected SS	380.345015	Corrected SS	379.723468
Coeff Variation	-2475.053	Std Error Mean	0.05273752

Basic Statistical Measures

Location		Variability	
Mean	-0.04099	Std Deviation	1.01443
Median	0.16987	Variance	1.02906
Mode	0.74219	Range	5.47903
		Interquartile Range	1.45931

Note: The mode displayed is the smallest of 2 modes with a count of 2.

FILE: normalitybc.lis, RUN: 18JUN2020 10:00
 PROGRAM: /opt/sas/Data/DAP/EB1020/P40520100013/STAT/Program.dev/DOC_STAT/normality.sas
 OPDC, NEW DRUG APPLICATION, IND # 119,361 CENTANAFADINE STAT-6.1.2 FINAL

CENTANAFADINE
 PROTOCOL 405-201-00013

30 OF 48

STAT-6.1.2
 Residual by Week from Proc Mixed for Change from Baseline in AISRS Total Score, Primary Efficacy Analysis Model
 (Efficacy Sample)

 ----- Analysis Visit (N)=28 -----

The UNIVARIATE Procedure
 Variable: STUDENTRESID (Studentized Residual)

Tests for Location: Mu0=0

Test	-Statistic-	-----p Value-----	
Student's t	t -0.77717	Pr > t	0.4376
Sign	M 25	Pr >= M	0.0108
Signed Rank	S 976.5	Pr >= S	0.6359

Tests for Normality

Test	--Statistic---	-----p Value-----	
Shapiro-Wilk	W 0.96038	Pr < W	<0.0001
Kolmogorov-Smirnov	D 0.09143	Pr > D	<0.0100
Cramer-von Mises	W-Sq 0.859455	Pr > W-Sq	<0.0050
Anderson-Darling	A-Sq 4.871	Pr > A-Sq	<0.0050

FILE: normalitybc.lis, RUN: 18JUN2020 10:00
 PROGRAM: /opt/sas/Data/DAP/EB1020/P40520100013/STAT/Program.dev/DOC_STAT/normality.sas
 OPDC, NEW DRUG APPLICATION, IND # 119,361 CENTANAFADINE STAT-6.1.2 FINAL

CENTANAFADINE
PROTOCOL 405-201-00013

31 OF 48

STAT-6.1.2
Residual by Week from Proc Mixed for Change from Baseline in AISRS Total Score, Primary Efficacy Analysis Model
(Efficacy Sample)

----- Analysis Visit (N)=28 -----

The UNIVARIATE Procedure
Variable: STUDENTRESID (Studentized Residual)

Quantiles (Definition 5)

Level	Quantile
100% Max	2.070287
99%	1.881686
95%	1.228575
90%	1.053543
75% Q3	0.747789
50% Median	0.169875
25% Q1	-0.711522
10%	-1.471843
5%	-2.092184
1%	-2.912932
0% Min	-3.408746

FILE: normalitybc.lis, RUN: 18JUN2020 10:00
PROGRAM: /opt/sas/Data/DAP/EB1020/P40520100013/STAT/Program.dev/DOC_STAT/normality.sas
OPDC, NEW DRUG APPLICATION, IND # 119,361 CENTANAFADINE STAT-6.1.2 FINAL

CENTANAFADINE
PROTOCOL 405-201-00013

32 OF 48

STAT-6.1.2
Residual by Week from Proc Mixed for Change from Baseline in AISRS Total Score, Primary Efficacy Analysis Model
(Efficacy Sample)

----- Analysis Visit (N)=28 -----

The UNIVARIATE Procedure
Variable: STUDENTRESID (Studentized Residual)

Extreme Observations

-----Lowest-----			-----Highest-----		
Value	USUBJID	Obs	Value	USUBJID	Obs
-3.40875	40520100013- [REDACTED]	1498	1.79657	40520100013- [REDACTED]	1519
-3.13286	40520100013- [REDACTED]	1517	1.88169	40520100013- [REDACTED]	1518
-3.10958	40520100013- [REDACTED]	1478	1.93934	40520100013- [REDACTED]	1344
-2.91293	40520100013- [REDACTED]	1372	1.97622	40520100013- [REDACTED]	1589
-2.80668	40520100013- [REDACTED]	1504	2.07029	40520100013- [REDACTED]	1341

FILE: normalitybc.lis, RUN: 18JUN2020 10:00
PROGRAM: /opt/sas/Data/DAP/EB1020/P40520100013/STAT/Program.dev/DOC_STAT/normality.sas
OPDC, NEW DRUG APPLICATION, IND # 119,361 CENTANAFADINE STAT-6.1.2 FINAL

CENTANAFADINE
 PROTOCOL 405-201-00013

33 OF 48

STAT-6.1.2
 Residual by Week from Proc Mixed for Change from Baseline in AISRS Total Score, Primary Efficacy Analysis Model
 (Efficacy Sample)

 ----- Analysis Visit (N)=35 -----

The UNIVARIATE Procedure
 Variable: RESID (Residual)

Moments

N	349	Sum Weights	349
Mean	-0.4303981	Sum Observations	-150.20894
Std Deviation	10.4068682	Variance	108.302907
Skewness	-0.5781918	Kurtosis	-0.263225
Uncorrected SS	37754.0612	Corrected SS	37689.4115
Coeff Variation	-2417.9632	Std Error Mean	0.55706689

Basic Statistical Measures

Location		Variability	
Mean	-0.43040	Std Deviation	10.40687
Median	1.66772	Variance	108.30291
Mode	-6.91304	Range	55.34813
		Interquartile Range	14.82125

Note: The mode displayed is the smallest of 5 modes with a count of 2.

FILE: normalitybc.lis, RUN: 18JUN2020 10:00

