Trial Duration:	A total of up to 1150 male and female subjects are planned to be screened in order to randomize approximately 450 subjects to yield approximately 292 completers. Individual participation for all subjects in the trial is 12 to 13 weeks, consisting of an up to 28-day screening period, a 1-week single-blind placebo run-in period, a 6-week double-blind treatment period, and a 7-day follow-up period (follow-up telephone calls at 1, 3, and 5 days after the last dose of IMP, and in-clinic visits 2 and 7 days after the last dose of IMP) for all subjects. For subjects who early terminate or decline participation in the open-label trial, they will be required to participate in an additional follow-up telephone call 10 days after the last dose of IMP.
-----------------	--

Protocol 405-201-00013

Table of Contents

Protocol Synopsis	2
Table of Contents	11
List of In-text Tables	16
List of In-text Figures	17
List of Appendices	18
List of Abbreviations and Definitions of Terms	19
1 Introduction	21
1.1 Nonclinical Data	22
1.2 Clinical Data	23
1.3 Known and Potential Risks and Benefits	23
2 Trial Rationale and Objectives	25
2.1 Trial Rationale	25
2.2 Dosing Rationale	25
2.3 Trial Objectives	26
3 Trial Design	26
3.1 Type/Design of Trial	26
3.2 Trial Treatments	29
3.2.1 Single-blind Placebo Run-in Period	29
3.2.2 Double-blind Treatment Period	29
3.3 Trial Population	30
3.3.1 Number of Subjects and Description of Population	30
3.3.2 Subject Selection and Numbering	30
3.4 Eligibility Criteria	31
3.4.1 Informed Consent	31
3.4.2 Inclusion Criteria	32
3.4.3 Exclusion Criteria	33
3.5 Endpoints	36
3.5.1 Primary Endpoint	36
3.5.1.1 Primary Efficacy Endpoint	36
3.5.2 Secondary Endpoints	36

Protocol 405-201-00013

3.5.2.1	Key Secondary Efficacy Endpoint	36
3.5.2.2	Other Efficacy Endpoints	36
3.5.3	Exploratory Endpoints	36
3.5.4	Safety Endpoints	36
3.6	Measures to Minimize/Avoid Bias	37
3.6.1	Randomization	37
3.7	Trial Procedures	37
3.7.1	Schedule of Assessments	41
3.7.1.1	Visit 1 (Screening)	41
3.7.1.2	Visit 2 (Single-blind Placebo Run-in)	42
3.7.1.3	Visit 3 (Baseline)	42
3.7.1.4	Double-Blind Treatment Period	43
3.7.1.4.1	Visits 4 through 8	43
3.7.1.4.2	Visit 9/End of Treatment/Early Termination	43
3.7.1.5	Visits 10 Through 14 (Follow-up)	44
3.7.1.6	Visit 15 (Follow-up)	45
3.7.2	Efficacy Assessments	45
3.7.2.1	Adult Attention-deficit/Hyperactivity Disorder Investigator Symptom Rating Scale	45

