3.7 Trial Procedures

The time from enrollment of the first subject to the last subject's last trial visit will be approximately 12 months. Individual participation for subjects who complete the trial will be approximately 12 weeks, consisting of a 28-day screening and washout period, a 1-week single-blind placebo run-in period, a baseline day, a 6-week double-blind treatment period, and a 7-day follow-up period (follow-up telephone calls at 1, 3, and 5 days after the last dose of IMP, and in-clinic visits 2 and 7 days after the last dose of IMP). For subjects who terminate early, decide to not enroll in Trial 405-201-00015, or who are not eligible to enroll in Trial 405-201-00015, they will be required to participate in the 7-day follow-up period as well as participate in an additional follow-up telephone call 10 days after the last dose of IMP.

When Trial 405-201-00013 reaches its conclusion, all subjects participating in the trial, regardless of trial period, may be eligible to enroll into Trial 405-201-00015, which is a 12-month, observational, open-label trial ([Section 3.1](#)). All subjects will be required to comply with the appropriate follow-up procedures described in [Section 3.7.1.5](#) and [Section 3.7.1.6](#).

Trial assessment time points are summarized in [Table 3.7-1](#) and [Table 3.7-2](#).

Protocol 405-201-00013

Table 3.7-1 Schedule of Assessments - Screening Through End of Treatment										
Period	Screening ^a	PBO Run-in ^b	Double-blind Treatment							NOTES
	Days -35 to -8	Day -7	Baseline Day -1	Day 7 +1 Day	Day 14 ±2 Days	Day 21 ±2 Days	Day 28 ±2 Days	Day 35 ±2 Days	Day 42/ET ±2 Days	
Visit	1	2	3	4	5	6	7	8	9	
ENTRANCE/HISTORY										
Informed consent	X									Section 3.4.1
Inclusion/exclusion criteria	X	X	X							Section 3.4
Demography	X									
Concomitant medication(s)	X	X	X	X	X	X	X	X	X	
Medical history	X	X	X							
ACDS	X									
Identification of comorbidities using MINI	X									
Psychiatric evaluation	X									
HIV/HBsAg/anti-HCV	X									Section 3.7.5.2
Randomization			X							Section 3.6.1
Urine pregnancy test	X	X	X	X	X	X	X	X	X	Section 3.7.5.2 Section 5.7
EFFICACY										
AISRS	X	X	X	X	X	X	X	X	X	Section 3.7.2.1
CGI-S			X	X	X	X	X	X	X	Section 3.7.2.2
CGI Change from Baseline				X	X	X	X	X	X	Section 3.7.2.3
SAFETY										
Adverse events	X	X	X	X	X	X	X	X	X	Section 5.2
Physical examination	X					X			X	Section 3.7.5.3.1
Vital signs	X	X	X	X	X	X	X	X	X	Section 3.7.5.3.2
12-lead ECG	X	X	X	X	X		X		X	Section 3.7.5.4

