3.7.1 Schedule of Assessments

3.7.1.1 Visit 1 (Screening)

The screening period begins after consent is obtained and will take place between Day -35 and Day -8 prior to the initiation of the single-blind placebo run-in period. Completion of screening activities may require more than 1 visit. All procedures outlined for screening in the Schedule of Assessments ([Table 3.7-1](#)) will be performed. The following should also be noted:

- The investigator or his/her designee must obtain informed consent from the subject prior to any trial-related procedures being performed.
- A urine drug screen will be collected and sent to the central lab for evaluation. If subjects are taking disallowed medications and they are able to taper appropriately and safely, they will do so during the screening period. If medication taken is for ADHD, a minimum of 7 days off stimulants and 21 days off nonstimulants will be required before the single-blind placebo run-in period. A complete washout schedule, including common excluded medications and herbal preparations, is provided in [Section 4.1](#). A subject who tested positive for any prohibited medications at the screening visit must have a repeat urine drug screen that is confirmed as negative prior to performing Visit 2.
- An assessment of all inclusion and exclusion criteria will be made to determine the subject's eligibility for the trial.
- Medical and psychiatric history will be recorded, including the DSM-5 diagnosis of ADHD using the ACDS Version 1.2.
- Subjects will be administered the ASRS.
- A urine pregnancy test will be performed for all females of childbearing potential (FOCBP). If the urine pregnancy test is positive, the result should be confirmed with a serum pregnancy test. Subjects with a positive serum test result will be excluded from the trial.

External quality oversight methods will be used by Clinical Surveillance & Training (CST) to promote appropriate subject enrollment. Such methods will require sites to communicate certain aspects of subject data during the screening period to CST as detailed in the Operations Manual. Subjects cannot be randomized until approval from CST has been received. The investigator is responsible for ensuring that subjects are eligible for enrollment into the trial and for assessing subject safety throughout the trial.

Protocol 405-201-00013

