3.7.1.3 Visit 3 (Baseline)

After the subject has completed the single-blind placebo run-in period, the Visit 3 (Day -1) assessments described in the Schedule of Assessments (Table 3.7-1) will be completed.

The following should also be noted:

- Urine drug screen results from the previous visit will be reviewed. If the subject is positive for any prohibited medications (including medications for the treatment of ADHD, see Section 4.1), the subject will be early terminated, and the procedures outlined in Section 3.7.1.4.2 will be completed.
- Subjects will be administered the ASRS, and those with a $\geq 30\%$ improvement in the (18-item) ADHD Symptoms score compared to the score at the start of single-blind placebo run-in will be early terminated.

Protocol 405-201-00013

- Subjects who do not meet eligibility (see Exclusion Criteria #30, #31, and #32) at the baseline visit are considered early termination subjects, and should proceed with the early termination visit ([Section 3.7.1.4.2](#)) and follow-up procedures ([Section 3.7.1.5](#) and [Section 3.7.1.6](#)).
- Dosing cards from the single-blind run-in period will be returned; accountability and compliance will be verified.
- Blood samples for genotyping and for future biospecimen research (FBR) will be collected.
- Subjects entering the double-blind treatment period will be randomized (1:1:1) to receive centanafadine SR 200 mg TDD, 400 mg TDD, or placebo.
- Subjects will receive a dosing card for dosing on Days 1 to 7, and will be instructed to start dosing from the new card on the following day (Day 1), and to take their doses at approximately the same time every day.

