Appendix 4 Criteria for Identifying Electrocardiogram Measurements of Potential Clinical Relevance

Variable	Criterion Value ^a	Change Relative to Baseline ^a
Rate		
Tachycardia	≥ 120 bpm	increase of ≥ 15 bpm
Bradycardia	≤ 50 bpm	decrease of ≥ 15 bpm
Rhythm		
Sinus tachycardia ^b	≥ 120 bpm	increase of ≥ 15 bpm
Sinus bradycardia ^c	≤ 50 bpm	decrease of ≥ 15 bpm
Supraventricular premature beat	all	not present → present
Ventricular premature beat	all	not present → present
Supraventricular tachycardia	all	not present → present
Ventricular tachycardia	all	not present → present
Atrial fibrillation	all	not present → present
Atrial flutter	all	not present → present
Conduction		
1° atrioventricular block	PR ≥ 200 msec	increase of ≥ 50 msec
2° atrioventricular block	all	not present → present
3° atrioventricular block	all	not present → present
Left bundle-branch block	all	not present → present
Right bundle-branch block	all	not present → present
Pre-excitation syndrome	all	not present → present
Other intraventricular conduction block ^d	QRS ≥ 120 msec	increase of ≥ 20 msec
Infarction		
Acute or subacute	all	not present → present
Old	all	not present → present ≥ 12 weeks post trial entry
ST/T Morphological		
Myocardial ischemia	all	not present → present
Symmetrical T-wave inversion	all	not present → present
Increase in QTc	QTcF > 450 msec (men) QTcF > 470 msec (women)	

^aIn order to be identified as potentially clinically relevant, an on-treatment value must meet the “Criterion Value” and also represent a change from the subject’s baseline value of at least the magnitude shown in the “Change Relative to Baseline” column.

^bNo current diagnosis of supraventricular tachycardia, ventricular tachycardia, atrial fibrillation, atrial flutter, or other rhythm abnormality.

^cNo current diagnosis of atrial fibrillation, atrial flutter, or other rhythm abnormality.

^dNo current diagnosis of left bundle branch block or right bundle branch block.

Protocol 405-201-00013

Appendix 5 Protocol Amendment(s)/Administrative Change(s)**Amendment Number:** 1**Issue Date:** 18 May 2018**PURPOSE:**

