Appendix 3 Criteria for Identifying ECG Measurements of Potential Clinical Relevance

Variable	Criterion Value ^a	Change Relative to Baseline ^a
Rate		
Tachycardia	≥ 120 bpm	increase of ≥ 15 bpm
Bradycardia	≤ 50 bpm	decrease of ≥ 15 bpm
Rhythm		
Sinus tachycardia ^b	≥ 120 bpm	increase of ≥ 15 bpm
Sinus bradycardia ^c	≤ 50 bpm	decrease of ≥ 15 bpm
Supraventricular premature beat	all	not present → present
Ventricular premature beat	all	not present → present
Supraventricular tachycardia	all	not present → present
Ventricular tachycardia	all	not present → present
Atrial fibrillation	all	not present → present
Atrial flutter	all	not present → present
Conduction		
1° atrioventricular block	PR ≥ 200 msec	increase of ≥ 50 msec
2° atrioventricular block	all	not present → present
3° atrioventricular block	all	not present → present
Left bundle-branch block	all	not present → present
Right bundle-branch block	all	not present → present
Pre-excitation syndrome	all	not present → present
Other intraventricular conduction block ^d	QRS ≥ 120 msec	increase of ≥ 20 msec
Infarction		
Acute or subacute	all	not present → present
Old	all	not present → present ≥ 12 weeks post study entry
ST/T Morphological		
Myocardial Ischemia	all	not present → present
Symmetrical T-wave inversion	all	not present → present
Increase in QTc	QTcF > 450 msec (men) QTcF > 470 msec (women)	

^a In order to be identified as potentially clinically relevant, an on-treatment value must meet the “Criterion Value” and also represent a change from the subject’s baseline value of at least the magnitude shown in the “Change Relative to Baseline” column.

^b No current diagnosis of supraventricular tachycardia, ventricular tachycardia, atrial fibrillation, atrial flutter, or other rhythm abnormality.

^c No current diagnosis of atrial fibrillation, atrial flutter, or other rhythm abnormality.

^d No current diagnosis of left bundle branch block or right bundle branch block.

SAP 405-201-00013

13 Proposed List of Summary Tables

- CT-1.1 Subject Disposition
- CT-1.2 Subject Disposition by Center
- CT-1.3 Subject Completion Rates by Week During the Double-Blind Treatment Period (Randomized Sample)
- CT-1.4.1 Subject Enrollment by Country (Randomized Sample)
- CT-1.4.2 Subject Enrollment by Country by Age Group (Randomized Sample)
- CT-2 Reasons for Discontinuation in the Double-Blind Treatment Period (Randomized Sample)
- CT-3.1 Demographic Characteristics (Randomized Sample)

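### The ECG row for a new old infarction needs the finding at least 12 weeks after trial entry, which no scheduled ECG can reach, so a zero in that row carries no information.

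*SAP*

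**What the plan says.** SAP Section 9.4.1 sends potentially clinically relevant ECG changes in the double-blind period to a listing and a by-arm summary (CT-12.2.1 and CT-12.2.2), using the criteria in SAP Appendix 3. In that appendix, the *Old* infarction row requires "not present → present ≥ 12 weeks post study entry". Protocol Appendix 4 has the same row with one word changed: "not present → present ≥ 12 weeks post trial entry". Footnote a in both appendices adds a second condition: "In order to be identified as potentially clinically relevant, an on-treatment value must meet the “Criterion Value", with the stated change from baseline as well.

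The timing comes from the protocol. Screening "will take place between Day -35 and Day -8" (Section 3.7.1.1). Table 3.7-1 schedules 12-lead ECGs at screening, Day -7, Day -1 and Days 7, 14, 28 and 42/ET, the last with the window "Day 42/ET ±2 Days". Table 3.7-2, the follow-up schedule, has no ECG row. Neither document defines study entry or trial entry.

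**The concern.** A tabulation rule with a 12-week minimum sits in a trial with six weeks of double-blind treatment. If no ECG can be late enough, the row is zero by construction. The reader of the ECG summary sees a zero in each arm, cannot tell it from a true absence, and finds no note that the row could not be assessed. Protocol Section 1.3 reports rises in blood pressure and heart rate and asks for caution in cardiovascular disease, so the cardiac rows are ones that a safety reviewer will look at. At stake is one row of the ECG tables. No efficacy result, QTc analysis or adverse event table depends on it.

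**Working it through.** **Counting rule.** At the Day -1 visit, subjects "will be instructed to start dosing from the new card on the following day (Day 1"). Day -1 is therefore followed by Day 1, and elapsed days = later day - earlier day - 1 whenever the span crosses from negative to positive days.

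**Reproducing the protocol's own timeline.** The synopsis gives 12 to 13 weeks of individual participation, "consisting of an up to 28-day screening period, a 1-week single-blind placebo run-in period, a 6-week double-blind treatment period" and a 7-day follow-up. 28 + 7 + 42 + 7 = 84 days = 12.0 weeks. The longest case is the 10 (+2)-day call after a last dose on Day 44, which is Day 56: 56 + 35 - 1 = 90 days = 12.9 weeks. The stated range is reproduced. It reaches 12 weeks only by including follow-up, when there is no ECG and no treatment.

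**Entry to the last ECG.** The criterion needs 12 × 7 = 84 days. Taking the earliest possible entry, Day -35:

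| To | Elapsed days | Weeks |
|---|---|---|
| Day 42 (nominal last ECG) | 42 + 35 - 1 = 76 | 10.9 |
| Day 44 (latest in window) | 44 + 35 - 1 = 78 | 11.1 |
| Day 47 (3 days after a Day 44 last dose) | 47 + 35 - 1 = 81 | 11.6 |
| Day 49 (end of the SAP's Day 42 window) | 49 + 35 - 1 = 83 | 11.9 |
| Day 50 | 50 + 35 - 1 = 84 | 12.0 |

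The latest scheduled ECG falls 84 - 78 = 6 days short. The Day 47 and Day 49 lines only stretch the point: the SAP's window rule (Section 10.1) names efficacy scales, not ECG, and Day 49 lies outside the protocol's visit window.

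**Other readings of entry.** Day -35 is the most generous. To Day 44, the span is 44 + 7 - 1 = 50 days (7.1 weeks) from the start of run-in, 44 + 1 - 1 = 44 days (6.3 weeks) from randomization on Day -1, and 44 - 1 = 43 days (6.1 weeks) from the first double-blind dose. Counting a Day 0 adds one day: 79 days (11.3 weeks).

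**One reading to rule out.** The full sentence in Section 3.7.1.1 says that screening "will take place between Day -35 and Day -8 prior to the initiation of the single-blind placebo run-in period". Read as 35 days before the run-in visit, entry would move back 7 days and the span would be 78 + 7 = 85 days, enough to pass. That reading fails. Table 3.7-1 puts screening (Days -35 to -8) on the same scale as the run-in visit (Day -7), and Days -35 to -8 are exactly the 28 days that the synopsis allows.

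**The case against.** The strongest reply is that the schedule does not bound real data. Section 3.7.5.4 asks for clinically significant abnormal ECGs to be repeated and sets no time for it, and entry is undefined. This part stands. A reader might infer that the criterion can never be met, or that the row has zero sensitivity for every subject. The documents support only the narrower statement about scheduled, in-window ECGs. An unscheduled ECG would have to fall on Day 50 or later, and on the planned calendar it would then fail the on-treatment condition. A rescreened subject signs a new consent and gets a new screening number, so entry restarts.

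A second reply is that the 12 weeks may be deliberate, to keep out infarcts that predate treatment. The requirement that the pattern be absent at baseline already does most of this, supported by three ECGs before double-blind dosing. No other row in the table has a time-since-entry condition. If the filter is intended, the row cannot be assessed in this design and should say so. The documents do not state where the 12 weeks came from, and nothing here depends on its origin.

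A third reply concerns consequences. A reader might infer that infarcts occurring between visits will be missed. The documents do not show this. They define no boundary between subacute and old and have no age-undetermined category. Acute or subacute infarction, myocardial ischemia and symmetrical T-wave inversion are separate rows without a time limit. ECG abnormalities that the investigator judges clinically significant are recorded as adverse events, serious events are tabulated and listed, and known ischemic heart disease or prior infarction is excluded (criterion 17). This reply stands and limits the point to one uninformative row.

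**Conclusion.** The point holds for scheduled ECGs. The longest span from entry to the last scheduled ECG is 78 days against 84, so the *Old* infarction row in CT-12.2.1 and CT-12.2.2 will be zero in every arm regardless of what those ECGs show. The same holds for the run-in versions, CT-12.4.1 and CT-12.4.2. The result rests on three assumptions: entry is no earlier than Day -35, the last ECG is within its ±2-day window, and the on-treatment condition in footnote a is applied. Every later definition of entry widens the gap. It is a modest defect in safety tabulation that is worth correcting; it is not evidence that cardiac events would go unrecorded.

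**What to change.** In SAP Appendix 3, for tabulation, remove the 12-week condition, so that an old infarction pattern absent at double-blind baseline and present on a double-blind ECG is counted. Alternatively, merge the two infarction rows into one row for any new infarction pattern. In the SAP this costs one line of text and one line of code.

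Protocol Appendix 4 must be reconciled with the ECG schedule. Section 3.7.5.4 also uses that appendix as a reference for monitoring subjects, so this change is more than an analysis edit, and the protocol's amendment policy (Section 13) applies.

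If the tables are already final, keep the row, footnote it as not assessable under the ECG schedule, and list any new infarction pattern regardless of timing. The downside of either route is that a few artefactual or pre-existing patterns may need comment.
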